### **7.2.4 Evaluating Adverse Events**

An investigator who is a qualified physician will evaluate all adverse events according to the NCI Common Terminology for Adverse Events (CTCAE), version 4. Any adverse event which changes CTCAE grade over the course of a given episode will have each change of grade recorded on the adverse event case report forms/worksheets.

All adverse events regardless of CTCAE grade must also be evaluated for seriousness.

For studies in which multiple agents are administered as part of a combination regimen, the investigator may attribute each adverse event causality to the combination regimen or to a single agent of the combination. In general, causality attribution should be assigned to the combination regimen (i.e., to all agents in the regimen). However, causality attribution may be assigned to a single agent if in the investigator's opinion, there is sufficient data to support full attribution of the adverse event to the single agent.

Table 10 Evaluating Adverse Events

An investigator who is a qualified physician, will evaluate all adverse events as to:

V4.0 CTCAE Grading	Grade 1	Mild; asymptomatic or mild symptoms; clinical or diagnostic observations only; intervention not indicated.
	Grade 2	Moderate; minimal, local or noninvasive intervention indicated; limiting age-appropriate instrumental ADL.
	Grade 3	Severe or medically significant but not immediately life-threatening; hospitalization or prolongation of hospitalization indicated; disabling; limiting self-care ADL.
	Grade 4	Life threatening consequences; urgent intervention indicated.
	Grade 5	Death related to AE
Seriousness	A serious adverse event is any adverse event occurring at any dose or during any use of Sponsor's product that:	
	† Results in death ; or	
	† Is life threatening ; or places the subject, in the view of the investigator, at immediate risk of death from the event as it occurred (Note: This does not include an adverse event that, had it occurred in a more severe form, might have caused death.); or	
	† Results in a persistent or significant disability/incapacity (substantial disruption of one's ability to conduct normal life functions); or	
	† Results in or prolongs an existing inpatient hospitalization (hospitalization is defined as an inpatient admission, regardless of length of stay, even if the hospitalization is a precautionary measure for continued observation. (Note: Hospitalization for an elective procedure to treat a pre-existing condition that has not worsened is not a serious adverse event. A pre-existing condition is a clinical condition that is diagnosed prior to the use of a Merck product and is documented in the patient's medical history.); or	
	† Is a congenital anomaly/birth defect (in offspring of subject taking the product regardless of time to diagnosis); or	
	Is a new cancer (that is not a condition of the study) (although not serious per ICH definition, is reportable to the Sponsor within 24 hours to meet certain local requirements); or	
	Is an overdose (whether accidental or intentional). Any adverse event associated with an overdose is considered a serious adverse event for collection purposes. An overdose that is not associated with an adverse event is considered a non-serious event of clinical interest and must be reported within 24 hours.	
	Other important medical events that may not result in death, not be life threatening, or not require hospitalization may be considered a serious adverse event when, based upon appropriate medical judgment, the event may jeopardize the subject and may require medical or surgical intervention to prevent one of the outcomes listed previously (designated above by a †).	
Duration	Record the start and stop dates of the adverse event. If less than 1 day, indicate the appropriate length of time and units	
Action taken	Did the adverse event cause the Sponsor's product to be discontinued?	
Relationship to Sponsor's Product	Did the Sponsor's product cause the adverse event? The determination of the likelihood that the Sponsor's product caused the adverse event will be provided by an investigator who is a qualified physician. The investigator's signed/dated initials on the source document or worksheet that supports the causality noted on the AE form, ensures that a medically qualified assessment of causality was done. This initialed document must be retained for the required regulatory time frame. The criteria below are intended as reference guidelines to assist the investigator in assessing the likelihood of a relationship between the test drug and the adverse event based upon the available information. The following components are to be used to assess the relationship between the Sponsor's product and the AE; the greater the correlation with the components and their respective elements (in number and/or intensity), the more likely the Sponsor's product caused the adverse event (AE):	
	Exposure	Is there evidence that the subject was actually exposed to the Sponsor's product such as: reliable history, acceptable compliance assessment (pill count, diary, etc.), expected pharmacologic effect, or measurement of drug/metabolite in bodily specimen?
	Time Course	Did the AE follow in a reasonable temporal sequence from administration of the Sponsor's product? Is the time of onset of the AE compatible with a drug-induced effect (applies to trials with investigational medicinal product)?
	Likely Cause	Is the AE not reasonably explained by another etiology such as underlying disease, other drug(s)/vaccine(s), or other host or environmental factors

Relationship to Sponsor's Product (continued)	The following components are to be used to assess the relationship between the test drug and the AE: (continued)	
	Dechallenge	Was the Sponsor's product discontinued or dose/exposure/frequency reduced? If yes, did the AE resolve or improve? If yes, this is a positive dechallenge. If no, this is a negative dechallenge. (Note: This criterion is not applicable if: (1) the AE resulted in death or permanent disability; (2) the AE resolved/improved despite continuation of the Sponsor's product; or (3) the trial is a single-dose drug trial); or (4) Sponsor's product(s) is/are only used one time.)
	Rechallenge	Was the subject re-exposed to the Sponsor's product in this study? If yes, did the AE recur or worsen? If yes, this is a positive rechallenge. If no, this is a negative rechallenge. (Note: This criterion is not applicable if: (1) the initial AE resulted in death or permanent disability, or (2) the trial is a single-dose drug trial); or (3) Sponsor's product(s) is/are used only one time). NOTE: IF A RECHALLENGE IS PLANNED FOR AN ADVERSE EVENT WHICH WAS SERIOUS AND WHICH MAY HAVE BEEN CAUSED BY THE SPONSOR'S PRODUCT, OR IF REEXPOSURE TO THE SPONSOR'S PRODUCT POSES ADDITIONAL POTENTIAL SIGNIFICANT RISK TO THE SUBJECT, THEN THE RECHALLENGE MUST BE APPROVED IN ADVANCE BY THE SPONSOR CLINICAL DIRECTOR AS PER DOSE MODIFICATION GUIDELINES IN THE PROTOCOL.
	Consistency with Trial Treatment Profile	Is the clinical/pathological presentation of the AE consistent with previous knowledge regarding the Sponsor's product or drug class pharmacology or toxicology?
The assessment of relationship will be reported on the case report forms /worksheets by an investigator who is a qualified physician according to his/her best clinical judgment, including consideration of the above elements.		
Record one of the following	Use the following scale of criteria as guidance (not all criteria must be present to be indicative of a Sponsor's product relationship).	
Yes, there is a reasonable possibility of Sponsor's product relationship.	There is evidence of exposure to the Sponsor's product. The temporal sequence of the AE onset relative to the administration of the Sponsor's product is reasonable. The AE is more likely explained by the Sponsor's product than by another cause.	
No, there is not a reasonable possibility of Sponsor's product relationship	Subject did not receive the Sponsor's product OR temporal sequence of the AE onset relative to administration of the Sponsor's product is not reasonable OR the AE is more likely explained by another cause than the Sponsor's product. (Also entered for a subject with overdose without an associated AE.)	

### 7.2.5 Sponsor Responsibility for Reporting Adverse Events

All Adverse Events will be reported to regulatory authorities, IRB/IECs and investigators in accordance with all applicable global laws and regulations, i.e., per ICH Topic E6 (R1) Guidelines for Good Clinical Practice.

### 7.2.6 Executive Oversight Committee

The Executive Oversight Committee (EOC) comprises members of Sponsor Senior Management. The EOC will receive and decide upon any recommendations made by the DMC regarding the trial.

### 7.2.7 Data Monitoring Committee

To supplement the routine trial monitoring outlined in this protocol, an external Data Monitoring Committee (DMC) will monitor the interim data from this trial. The voting members of the committee are external to the Sponsor. The members of the DMC must not be involved with the trial in any other way (e.g., they cannot be trial investigators) and must have no competing interests that could affect their roles with respect to the trial.

The DMC will make recommendations to the EOC regarding steps to ensure both subject safety and the continued ethical integrity of the trial. Also, the DMC will review interim trial results, consider the overall risk and benefit to trial participants (see Section 8.7 - Interim Analyses) and recommend to the EOC if the trial should continue in accordance with the protocol.

Specific details regarding composition, responsibilities, and governance, including the roles and responsibilities of the various members and the Sponsor protocol team; meeting facilitation; the trial governance structure; and requirements for and proper documentation of DMC reports, minutes, and recommendations will be described in the DMC charter that is reviewed and approved by all the DMC members.

The DMC has responsibility for assessment of the overall risk:benefit. Periodic safety monitoring will be specified in the DMC Charter with input from the DMC members. When prompted by safety concerns, the DMC can request corresponding efficacy data. Any DMC recommendation will be communicated to the Sponsor as agreed to in the DMC Charter. As of Amendment 06, no additional DMC reviews will take place.

## 8.0 STATISTICAL ANALYSIS PLAN

**NOTE: Data from the IA1 of KEYNOTE-598 (data cutoff: 01-SEP-2020) indicated that the study did not meet the prespecified success criteria for improvement in PFS or OS for the combination of pembrolizumab plus ipilimumab compared with pembrolizumab plus placebo. Furthermore, a nonbinding futility analysis was performed at IA1 at the request of the eDMC. This analysis showed the study met the criteria for declaring futility and the benefit-risk was not considered positive to continue the trial. Based upon these data and at the recommendation of the eDMC, no further prespecified analysis of primary and secondary endpoints will be performed. Exploratory objectives may not be pursued. Updates to the safety analyses are provided in Sec. 8.1 and Sec. 8.6.2.**

This section outlines the statistical analysis strategy and procedures for the study. If, after the study has begun, changes are made to primary and/or key secondary hypotheses or the statistical methods related to those hypotheses, but prior to any unblinding/final database lock, then the protocol will be amended (consistent with ICH Guideline E9). Changes to exploratory or other nonconfirmatory analyses made after the protocol has been finalized, but prior to unblinding/final database lock, will be documented in a supplemental SAP (sSAP) and referenced in the Clinical Study Report (CSR) for the study. Post hoc exploratory analyses will be clearly identified in the CSR. Separate analysis plans (i.e., separate documents from the sSAP) will be developed to detail PK analysis as well as biomarker analysis. The PRO analysis plan will be included in the sSAP.

### 8.1 Statistical Analysis Plan Summary

Key elements of the SAP are summarized in this section. The comprehensive plan is provided in Section 8.2 – Responsibility for Analyses/In-House Blinding through Section 8.12 – Extent of Exposure.

Study Design Overview	Phase 3 study of Pembrolizumab + Ipilimumab versus Pembrolizumab + placebo in 1L, Stage IV, metastatic NSCLC subjects whose tumors express PD-L1 (TPS $\geq$ 50%).
Treatment Assignment	Subjects will be randomized in a 1:1 ratio between 2 treatment arms: (1) pembrolizumab plus ipilimumab and (2) pembrolizumab plus placebo. Stratification factors are as follows: 1) ECOG Performance Status (0 versus 1) 2) Geographic region (East Asia versus Non-East Asia) 3) Predominant tumor histology (squamous versus nonsquamous)
Analysis Populations	Efficacy: Intent-to-Treat (ITT) Safety: All Subjects as Treated (ASaT)
Primary Endpoints/Hypotheses	
 
• OS
 
• PFS per RECIST 1.1 based on BICR
 

Secondary Endpoints	
 
• ORR per RECIST 1.1 based on BICR
 
• DOR
 
• Safety and tolerability
 
• Change from baseline in global health status/quality of life score from the EORTC QLQ-C30 (items 29 and 30)
 
• TTD in PRO composite endpoint
 

Statistical Methods for Key Efficacy Analyses	The primary hypotheses will be evaluated by comparing pembrolizumab plus ipilimumab to pembrolizumab plus placebo in PFS and OS using a stratified log-rank test. The hazard ratio will be estimated using a stratified Cox regression model. Event rates over time will be estimated within each treatment group using the Kaplan-Meier method. The ORR will be evaluated using a stratified Miettinen and Nurminen method with strata weighting by sample size [40].
Statistical Methods for Key Safety Analyses	As of Amendment 06, the safety analysis will include only the proportion of participants with certain AEs summarized by counts and percentages by treatment group.

Interim Analyses	
As of Amendment 06, IA1 is complete. The other prespecified analyses listed below will not be performed.
 
Two efficacy IAs and one FA are planned in this study. Results will be reviewed by an external DMC. Details are provided in Section 8.7 – Interim Analyses.
 
 
• Interim analysis 1 (IA1): Approximately 255 deaths have been observed and ~ 12 months after the last subject randomized. The ORR p-value from IA1 may be evaluated for statistical significance if the PFS and/or OS null hypotheses are rejected at IA1 or a later time.                         
 
○ Purpose: Interim PFS (~ 92% of target PFS events) and OS analyses (~ 71% of target OS events).
 
 
 
• Interim analysis 2 (IA2): Approximately 307 deaths have been observed and ~ 19 months after the last subject randomized.                         
 
○ Purpose: Final PFS analysis and interim OS analysis (~ 85% of target OS events).
 
 
 
• Final analysis (FA): Approximately 361 deaths have been observed and ~ 27 months after the last subject randomized.                         
 
○ Purpose: Final OS analysis.
 
 
 

Multiplicity	
The overall Type I error rate over the multiple endpoints will be strongly controlled at 2.5% (one-sided). A 0.6% (one-sided) Type I error rate will be allocated to test PFS and 1.9% (one-sided) allocated to test OS. The graphical method of Maurer and Bretz [41] will be applied to reallocate alpha between the hypotheses of ORR, PFS and OS. Group sequential methods will be used to allocate alpha between the interim and final analyses for the PFS and OS endpoints.

Sample Size and Power	
The planned sample size is approximately 568 subjects. With 389 PFS events, the study has ~ 87% power for detecting a hazard ratio of 0.69 at 0.6% (one-sided) significance level. With 361 deaths, the study has ~ 90% power for detecting a hazard ratio of 0.7 at 1.90 % (one-sided) significance level.

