### 8.8.1 Objective Response Rate

No initial alpha is allocated to test ORR. However, the ORR p-value from IA1 (ie, no new data is added after IA1) can be compared to an  $\alpha$ -level of eg, 0.025 if the null hypotheses for both PFS and OS are rejected at IA1 or a later time. The power at the updated  $\alpha$ -level of 0.025 is 99.8%, with an approximate treatment difference ( $\Delta$ ORR) required for reaching the efficacy bound being 8.1%, assuming underlying 39% and 59% ORR in the control and experimental groups, respectively.

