### 8.8.2 Progression-free Survival

The trial initially allocates  $\alpha=0.006$ , one-sided, to test PFS. If the null hypothesis for OS is rejected, its  $\alpha=0.019$  is essentially fully reallocated to PFS hypothesis testing. Thus, the PFS null hypothesis may be tested at  $\alpha=0.006$  or eg.  $\alpha=0.025$  (if both ORR and OS null hypotheses are rejected). Table 15 below shows the boundary properties for each of these  $\alpha$ -levels for the IAs and FA, which were derived using a Lan-DeMets O'Brien-Fleming spending function. Note that the final row indicates the total power to reject the null hypothesis for PFS at each  $\alpha$ -level. Also note that if the OS null hypothesis is rejected at an IA or FA, each PFS IA and FA test may be compared to its updated bounds considering the  $\alpha$  reallocation from the OS hypothesis.

Table 15 Efficacy Boundaries and Properties for Progression-free Survival Analyses

Analysis	Value	$\alpha=0.006$	$\alpha=0.025$
IA1: 92% a N: 568 Events: 357 Month: ~ 32 f	Z	2.6394	2.0667
	p (1-sided) b	0.0042	0.0194
	HR at bound c	0.7562	0.8034
	P(Cross) if HR=1 d	0.0042	0.0194
	P(Cross) if HR=0.69 e	0.8085	0.9251
IA2: Final PFS Analysis N: 568 Events: 389 Month: ~ 39 f	Z	2.5869	2.0575
	p (1-sided) b	0.0048	0.0198
	HR at bound c	0.7690	0.8115
	P(Cross) if HR=1 d	0.0060	0.0250
	P(Cross) if HR=0.69 e	0.8692	0.9517
a Percentage of total planned events at each interim analysis. b The nominal $\alpha$ for testing. c The approximate HR required to reach an efficacy bound d The probability of crossing a bound under the null hypothesis e The probability of crossing a bound under the alternative hypothesis f The approximate number of months since first subject randomized			

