### 8.8.3 Overall Survival

The OS hypothesis may be tested at  $\alpha=0.019$  or eg.  $\alpha=0.025$  (if both ORR and PFS null hypotheses are rejected). [Table 16](#), analogous to the PFS table explained above, demonstrates the boundary properties for each of these  $\alpha$ -levels for the IAs and FA, which were derived using a Lan-DeMets O'Brien-Fleming spending function. Note that if the PFS null hypothesis is rejected at an IA, each OS interim and final analysis test may be compared to its updated bounds considering the  $\alpha$  reallocation from the PFS hypothesis.

Table 16 Efficacy Boundaries and Properties for Overall Survival Analyses

Analysis	Value	$\alpha=0.019$	$\alpha=0.025$
IA1: 71% a N: 568 Events: 255 Month: ~ 32 f	Z	2.5592	2.4257
	p (1-sided) b	0.0052	0.0076
	HR at bound c	0.7256	0.7378
	P(Cross) if HR=1 d	0.0052	0.0076
	P(Cross) if HR=0.7 e	0.6135	0.6631
IA2: 85% a N: 568 Events: 307 Month: ~ 39 f	Z	2.3490	2.2316
	p (1-sided) b	0.0094	0.0128
	HR at bound c	0.7646	0.7750
	P(Cross) if HR=1 d	0.0110	0.0151
	P(Cross) if HR=0.7 e	0.7900	0.8228
FA g : N: 568 Events: 361 Month: ~ 47 f	Z	2.1577	2.0504
	p (1-sided) b	0.0155	0.0202
	HR at bound c	0.7967	0.8058
	P(Cross) if HR=1 d	0.0190	0.0250
	P(Cross) if HR=0.7 e	0.8985	0.9167
a Percentage of total planned events at each interim analysis. b The nominal $\alpha$ for testing. c The approximate HR required to reach an efficacy bound d The probability of crossing a bound under the null hypothesis e The probability of crossing a bound under the alternative hypothesis f The approximate number of months since first subject randomized g FA will be conducted at 34 months after the enrollment of the last participant at the latest, if the event accumulation is slower than expected.			

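### Do the rules for passing alpha among ORR, PFS and OS contradict each other and leave the PFS threshold open after an OS win?

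*Combined protocol and SAP*

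**What the plan says.** Section 8.8 controls one-sided error at 0.025 with the Maurer-Bretz graphical method. It states that Figure 4 shows the starting alpha of each hypothesis and, on the connecting lines, the weights for passing it on. The starting values are also in prose. Section 8.1: "A 0.6% (one-sided) Type I error rate will be allocated to test PFS and 1.9% (one-sided) allocated to test OS". Section 8.8.1: "No initial alpha is allocated to test ORR".

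The statements about passing alpha on are these:

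- **Section 8.1 (summary table):** the IA1 p-value for ORR "may be evaluated for statistical significance if the PFS and/or OS null hypotheses are rejected at IA1 or a later time". No level is given.
- **Section 8.8.1:** ORR may be compared with a level, marked *eg*, of 0.025 "if the null hypotheses for both PFS and OS are rejected at IA1 or a later time".
- **Section 8.8.2:** after an OS rejection its 0.019 "is essentially fully reallocated to PFS hypothesis testing". PFS may be tested at 0.006 or, again marked *eg*, at 0.025 ("if both ORR and OS null hypotheses are rejected"). The section closes by saying that once OS is rejected, the PFS tests may be held against updated bounds that reflect the alpha received from OS.
- **Section 8.8.3:** OS may be tested at 0.019 or *eg* 0.025 ("if both ORR and PFS null hypotheses are rejected"), with a matching sentence on updated bounds after a PFS rejection.

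Tables 15 and 16 give bounds at the starting alpha and at 0.025. Section 8.1 describes itself as a summary and refers to Sections 8.2 to 8.12 for the full plan.

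**The concern.** Section 8.1 seems to open ORR after either primary endpoint, and Section 8.8.1 only after both. If ORR really had to wait for both, the 0.025 columns of Tables 15 and 16 could never decide anything. Their condition includes an ORR rejection, and by then PFS and OS would already have been rejected. Section 8.8.2 also seems to disagree with itself: one sentence lets an OS win alone move the alpha, and the next adds an ORR condition.

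Two things would be at stake. The first is the PFS threshold after an OS win. Table 15 gives a final nominal p of 0.0048 (HR bound 0.7690, power 0.8692) at 0.006, and 0.0198 (0.8115, 0.9517) at 0.025. The second is double use of alpha. If OS alone were rejected and its 0.019 went in full to PFS and again in full to ORR, the chance of a false PFS or ORR claim under independence would be 1 − 0.975 × 0.981 = 0.0435. At correlations of 0.3 and 0.5 it would be 0.0421 and 0.0402. The plan promises 0.025.

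**Working it through.** **1. The plan's own figures.** Inputs: 357 and 389 PFS events, HR 0.69; 255, 307 and 361 deaths, HR 0.7 (Tables 15 and 16); 284 per arm (568, 1:1) with ORR 39% and 59% (Section 8.8.1). With Lan-DeMets O'Brien-Fleming spending and HR bound = exp(−2Z/√events):

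- Alpha split: 0.006 + 0.019 = 0.025.
- PFS power: 0.8683 and 0.9518 (Table 15: 0.8692 and 0.9517).
- Final PFS nominal p: 0.0048 and 0.0198, as stated. HR bounds: 0.7693 and 0.8117 (Table 15: 0.7690 and 0.8115).
- OS power: 0.8984 and 0.9168 (Table 16: 0.8985 and 0.9167).
- ORR at 0.025: power 99.8% and difference at the bound 8.1%, as stated.

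**2. One graph for all the statements.** Assume each primary endpoint passes a share 1 − e to the other and a small share e to ORR, and that ORR passes g to PFS and 1 − g to OS. The values e and g are assumptions. The standard update rule gives:

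- *OS rejected alone:* PFS = 0.006 + 0.019(1 − e) and ORR = 0.019e. ORR is open at a small level, and PFS has received essentially all of the OS alpha.
- *PFS rejected alone:* OS = 0.019 + 0.006(1 − e) and ORR = 0.006e.
- *OS, then ORR:* after the OS rejection the ORR-to-PFS weight is [g + (1 − g)(1 − e)] / [1 − (1 − g)e] = 1 for any g. So PFS = 0.006 + 0.019(1 − e) + 0.019e = 0.025 exactly. OS after PFS and ORR follows in the same way.
- *OS and PFS:* after the OS rejection the PFS-to-ORR weight is [e + (1 − e)e] / [1 − (1 − e)²] = 1. So ORR = 0.025 exactly.

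These match Sections 8.1, 8.8.1, 8.8.2 and 8.8.3 in turn. Section 8.1 says when ORR opens. Section 8.8.1 gives its level once both primaries are rejected and does not say ORR must wait until then.

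**3. How far the PFS threshold depends on e.**

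| e | PFS level after OS alone | final nominal p | HR bound | ORR level after OS alone | ORR power at that level |
|---|---|---|---|---|---|
| 0.001 | 0.024981 | 0.0198 | 0.8117 | 0.000019 | 75% |
| 0.01 | 0.02481 | 0.0197 | 0.8114 | 0.00019 | 89% |
| 0.1 | 0.0231 | 0.0183 | 0.8091 | 0.0019 | 97% |

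At exactly 0.025 the recomputed HR bound is 0.8117. The ORR power shows that the 0.025 column can matter: OS can win, ORR can be rejected at its small level, and PFS is then tested at exactly 0.025.

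**4. Circularity.** Testing starts at PFS 0.006 and OS 0.019 and needs no prior ORR result. Loops are normal in these graphs, and the final set of rejections does not depend on the order of updating.

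**5. Familywise error.** A single-look simulation (200,000 runs per case, independent p-values, e = 0.001 and 0.1, g = 0.5) covered seven patterns of true and false nulls. It gave 0.0244 to 0.0255. The standard error at 0.025 is √(0.025 × 0.975 / 200,000) = 0.00035, so every value is within two standard errors of 0.025. Testing ORR at the full 0.025 after either primary alone would inflate the error: 1 − 0.981 × 0.975 = 0.0435 if only PFS has a true effect, and 1 − 0.994 × 0.975 = 0.0309 if only OS does. No section prescribes that.

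**The case for a change.** The best case on the other side is that the prose and tables cover the starting state and the state after two rejections, but not the state after one primary rejection, which is where recycling matters most. Section 8.8.2 draws from a premise about OS alone a conclusion that also requires ORR. Section 8.8.3 has no counterpart to the statement that the alpha moves almost completely. Updated bounds are promised but not tabulated for a single rejection. The reconciliation needs a share e that the prose never states, and over e = 0.001 to 0.1 the ORR level after OS alone varies 100-fold, from 0.000019 to 0.0019.

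Part of this stands. The prose does not repeat the share, so a reader without Figure 4 cannot derive the ORR level after one rejection. But the plan places the weights in Figure 4, and a missing image in the text available here is not an omission from the plan. The *eg* markers show that 0.025 is one example level among others. The updated-bounds sentences rule out staying at 0.006 after an OS win, so the contrast between 0.0048 and 0.0198 is not a live ambiguity. For OS after PFS alone the level is 0.024994, 0.02494 or 0.0244 at the three shares, again close to the tabulated 0.025. The 4.0% to 4.4% error needs alpha to be spent twice, which the graphical method excludes.

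**Conclusion.** The concern does not hold. The statements in Sections 8.1 and 8.8.1 to 8.8.3 are compatible with one standard graph that keeps familywise error at 0.025, and the loop through ORR is not a circular definition. After an OS win alone, PFS is judged close to the 0.025 column of Table 15, with an HR bound of 0.809 to 0.812 for any ORR share up to 0.1. If the share were exactly zero, PFS would move to exactly 0.025. The ORR condition in Sections 8.8.2 and 8.8.3 and the wider trigger in Section 8.1 would then be loose wording, with the PFS threshold unchanged.

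This rests on assumed shares, because the values in Figure 4 could not be read. The qualified wording in Section 8.8.2 on how completely the OS alpha moves points to a small share. The error check is single-look with independent p-values. Changing Section 8.1 to require both rejections, or removing the ORR condition from Sections 8.8.2 and 8.8.3, could make the text contradict a prespecified figure.

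What remains is missing detail in the prose, with no effect on any result. Under Amendment 06, neither PFS nor OS met its criterion at IA1 and no further prespecified primary or secondary analysis will be done, so no alpha has been or will be passed on.
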